1 STUDY FLOW CHART

Zydus Discovery DMCC

CLINICAL TRIAL PROTOCOL

Saroglitazar Magnesium – Phase II

SARO.16.004

Confidential
Page 21 of 82

Approved by:
[name]

Protocol No. SARO.16.004
Version No.: 6.0

Zydus Discovery DMCC

CLINICAL TRIAL PROTOCOL

Saroglitazar Magnesium – Phase II

SARO.16.004

Confidential
Page 22 of 82

Approved by:
[name]

Protocol No. SARO.16.004
Version No.: 6.0

Zydus Discovery DMCC

CLINICAL TRIAL PROTOCOL
Saroglitzazar Magnesium – Phase II
SARO.16.004

Confidential
Page 23 of 82

Approved by:
[name]

Protocol No. SARO.16.004
Version No.: 6.0

Zydus Discovery DMCC

CLINICAL TRIAL PROTOCOL

Saroglitzaz Magnesium – Phase II

SARO.16.004

Confidential
Page 24 of 82

Approved by:
[name]

Protocol No. SARO.16.004
Version No.: 6.0

2 INTRODUCTION

2.1 MEDICAL BACKGROUND

Primary biliary Cholangitis (PBC) previously referred as “Primary biliary cirrhosis (PBC)” is a chronic progressive inflammatory autoimmune mediated cholestatic disease that mainly affects middle age women and is characterized by progressive inflammatory destruction of the interlobular bile duct, and the subsequent development of liver fibrosis and cirrhosis, eventually leading to liver failure (Ulrich et al., 2015; Keith et al., 2009; EASL 2009). Fatigue (65% to 85% of patients) and pruritus (25 – 70% of patients) are the most prevalent symptoms and have a major impact on quality of life (QoL). Additionally Hyperlipidaemia arises in up to 85% of patients, and could be the initial serum abnormality in PBC (Jayant and Keith, 2003).

The etiology and exact pathogenesis of PBC are still not clear, and proposed to be related with genetic factors, viral and bacterial infections, autoimmune status, and environmental factors. At present ursodeoxycholic acid (UDCA) and obeticholic acid (OCA) are approved therapeutic options for the treatment of PBC. But, up to 40% of UDCA-treated patients have an inadequate biochemical response, depending on the criteria used, and such patients have significantly worse transplant-free survival rates than UDCA-responsive patients (Gideon et al., 2015). Recently, OCA has been approved for use in PBC patients who are UDCA unresponsive or intolerant. However, OCA is associated with an increase in pruritus and its tolerability may be sub-optimal in the real world. In the POISE trial, pruritus occurred more frequently in the OCA-treated groups relative to placebo, with 38%, 56%, and 68% of patients experiencing pruritus in the placebo, 5-10 mg, and 10 mg groups, respectively. Adverse changes in lipid levels, mostly due to reductions in high-density lipoprotein (HDL), were also common in all OCA-treated patients. Although, it is unclear if these changes by themselves are of any clinical significance (Nevens et al., 2014), the presence of additional risk factors such as smoking and family history of cardiovascular disease is of concern.

2.2 RATIONALE FOR CONDUCTING THE TRIAL

A growing body of literature supports the notion that nuclear receptors are critically involved in the regulation of hepatic bile salt secretion and bile formation. In particular, PPAR α which

is highly expressed in liver, muscle, kidney and heart regulates the transcription of several genes involved in lipid metabolism, cholesterol and bile acid homeostasis through inhibition of cytochrome P450 cholesterol 7A1-hydroxylase (CYP7A1), the rate limiting step in bile acid synthesis.

PPAR α is the molecular target for the fibrate hypolipidemic agents, including fenofibrate, gemfibrozil and clofibrate, which are FDA-approved for the treatment of dyslipidemia, though each fibrate differs in its specificity for the different PPAR subtypes, α , β/δ and γ . Fibrates were first noted to reduce hepatic alkaline phosphatase (ALP) isoenzyme levels during their development as cholesterol-lowering agents in the 1970s (Zumoff 1977). Since then, case reports and pilot studies demonstrated the efficacy of bezafibrate and fenofibrate in reducing the biomarkers of cholestasis and liver test abnormalities (Ghoneim et al., 2015). A recent study reported significantly higher decompensation-free and transplant-free survival in patients treated with fenofibrate and UDCA when compared to UDCA alone (Cheung et al., 2016).

Saroglitazar magnesium [REDACTED], a dual PPAR agonist with predominantly PPAR α and a moderate PPAR γ agonist, is approved in India at the doses of 2 mg and 4 mg QD for the treatment of “diabetic dyslipidemia” and “hypertriglyceridemia with type 2 diabetes mellitus (T2DM) not controlled by statin therapy”. Saroglitazar magnesium Phase 2 and 3 studies in patients with dyslipidemia with and without diabetes, and in patients with NASH demonstrated potential of favorably modulating the predicting markers of PBC (alkaline phosphate and Gamma-glutamyl transferase) in addition to its anti-hypertriglyceridemia activity.

There is a strong mechanistic rationale for studying PPAR α/γ agonist in PBC, therefore, this proof of concept placebo-controlled Phase 2 study is designed to evaluate the Safety, Tolerability and Efficacy of Saroglitazar magnesium (2 mg and 4 mg) in Patients with PBC.

Pre-clinical Experience

[REDACTED]

[REDACTED]

[REDACTED]

[REDACTED]	[REDACTED]	[REDACTED]	[REDACTED]	[REDACTED]
[REDACTED]	[REDACTED]	[REDACTED]	[REDACTED]	[REDACTED]
[REDACTED]	[REDACTED]	[REDACTED]	[REDACTED]	[REDACTED]
[REDACTED]	[REDACTED]	[REDACTED]	[REDACTED]	[REDACTED]
[REDACTED]	[REDACTED]	[REDACTED]	[REDACTED]	[REDACTED]
[REDACTED]	[REDACTED]	[REDACTED]	[REDACTED]	[REDACTED]
[REDACTED]	[REDACTED]	[REDACTED]	[REDACTED]	[REDACTED]

[REDACTED]	[REDACTED]	[REDACTED]	[REDACTED]	[REDACTED]
[REDACTED]	[REDACTED]	[REDACTED]	[REDACTED]	[REDACTED]
[REDACTED]	[REDACTED]	[REDACTED]	[REDACTED]	[REDACTED]
[REDACTED]	[REDACTED]	[REDACTED]	[REDACTED]	[REDACTED]
[REDACTED]	[REDACTED]	[REDACTED]	[REDACTED]	[REDACTED]
[REDACTED]	[REDACTED]	[REDACTED]	[REDACTED]	[REDACTED]
[REDACTED]	[REDACTED]	[REDACTED]	[REDACTED]	[REDACTED]

Clinical Experience

Maximum Tolerated Dose in Phase 1 was 16 mg/day for 10 days was found to be well tolerated. In Phase I trials in healthy human volunteers, Saroglitazar magnesium was found to be well tolerated in single[Jani et al., 2013] and multiple dose studies without any safety concern. Several Phase 2 study were conducted to evaluate the safety and efficacy of Saroglitazar magnesium in dyslipidemic subjects without diabetes, diabetes and subjects with impaired glucose tolerance test.

In dyslipidemic subjects with and without diabetes mellitus, Saroglitazar magnesium showed favorable results in all the expected endpoints (fasting plasma glucose: (FPG) and lipid profile). Saroglitazar magnesium, especially 2 mg Saroglitazar magnesium and 4 mg Saroglitazar magnesium seemed to be comparable to pioglitazone and rosiglitazone and showed clinically relevant reduction in the TG-C, total cholesterol and FPG levels. Saroglitazar magnesium has been tested in Phase 2 for NASH at 4 mg dosage form and demonstrated statistically significant reduction of ALT levels compared to placebo which was measured as the primary endpoint. [REDACTED]

2.3 DRUG PROFILE

**Zydus Discovery
DMCC**

CLINICAL TRIAL PROTOCOL

Saroglitzaz Magnesium – Phase II

SARO.16.004

CONFIDENTIAL

PAGE 29 OF 82

2.4 RISK AND BENEFIT

The safety and tolerability of Saroglitzaz magnesium is well-established on the basis of pre-clinical and clinical studies (Phase 1 to Phase 3). This study will evaluate the safety and efficacy of Saroglitzaz magnesium in Primary Biliary Cholangitis patients. The commonly reported adverse events (AEs) during clinical studies were gastritis, asthenia and pyrexia.

Saroglitzaz magnesium is approved in India at doses of 2 mg and 4 mg QD for the treatment of “diabetic dyslipidemia” and “hypertriglyceridemia with T2DM not controlled by statin therapy”.

Approved by:
[name]

Protocol No. SARO.16.004
Version No.: 6.0

3 STUDY OBJECTIVES

The purpose of this study is to evaluate the safety, tolerability and efficacy of Saroglitzaz magnesium in patients with Primary Biliary Cholangitis.

3.1 PRIMARY OBJECTIVES

1. To investigate the effect of a 16-week treatment regimen of Saroglitzaz magnesium 2 mg and 4 mg on ALP levels in patients with Primary Biliary Cholangitis.

3.2 SECONDARY OBJECTIVES

1. To compare the effect of Saroglitzaz magnesium (2 mg and 4 mg) and placebo on below mentioned parameters following a 16-week treatment:
 - i. Alkaline Phosphatase
 - ii. Lipids profile: TG, TC, HDL, LDL, and VLDL
 - iii. Liver biochemistries: GGT, ALT, AST, bilirubin and albumin.
 - iv. Serum total bile acids
 - v. 7 α -hydroxy-4-cholest-3-one (C4)
 - vi. Fibroblast growth factor 19 (FGF19)
2. Proportion of patients with ALP improvement.
3. Quality of life by using (PBC40; Jacoby et al., 2005).
4. Safety and tolerability of Saroglitzaz magnesium 2 mg and 4 mg.
5. Pharmacokinetics of Saroglitzaz.

3.3 SAFETY ASSESSMENT

To assess the safety of Saroglitzaz magnesium in the study population over the duration of study.

- Frequency and severity of adverse events
- Clinical laboratory testing (hematology, clinical chemistry and urinalysis)
- Twelve-lead electrocardiogram (ECG)
- Vital signs

**Zydus Discovery
DMCC**

CLINICAL TRIAL PROTOCOL

Saroglitzaz Magnesium – Phase II

SARO.16.004

CONFIDENTIAL

PAGE 31 OF 82

- Body weight and height (at screening)
- The physical examination will consist of an evaluation of the head, neck, eyes, ears, nose, throat, chest, heart, lungs, abdomen, skin, extremities, and the neurological and musculoskeletal systems.

Approved by:
[name]

Protocol No. SARO.16.004
Version No.: 6.0

4 STUDY POPULATION

4.1 NUMBER OF SUBJECTS PLANNED

A total 36 subjects (including 20% dropout), will be enrolled on competitive basis at ~10-12 sites in a ratio of 1:1:1 to have 12 subjects in each arm i.e., Saroglitzaz magnesium 2 mg, Saroglitzaz magnesium 4 mg and placebo. Six patients in each group are planned for pharmacokinetic assessment therefore a total of 18 patients will be included. Additional patients may be enrolled into the study to ensure the pharmacokinetic assessment is performed on at least 6 completed patients in each treatment arm. Additional patients will be enrolled if the dropout rate is more than 20%.

4.2 INCLUSION CRITERIA

1. Males or females, between 18 and 75 years of age, inclusive.
2. a) Patients on therapeutic doses of Ursodeoxycholic acid (UDCA) for ≥ 12 months and stable therapy for ≥ 3 months prior to enrolment.
OR
b) Patients who are unable to tolerate UDCA, and did not receive UDCA for at least 3 months from the date of screening.
3. History of confirmed Primary Biliary Cholangitis Diagnosis, based on American Association for the Study of Liver Disease [AASLD] and European Association for Study of the Liver [EASL] Practice Guidelines; [Lindor 2009; EASL 2009], as demonstrated by the presence of at least ≥ 2 of the following 3 diagnostic factors:
 - History of elevated Alkaline Phosphatase levels for at least 6 months prior to Screening Visit 1
 - Positive antimitochondrial antibodies (AMA) titer or if AMA negative or in low titer ($<1:80$) PBC specific antibodies (anti-GP210 and/or anti-SP100 and/or antibodies against the major M2 components [PDC-E2, 2-oxo-glutaric acid dehydrogenase complex])
 - Liver biopsy consistent with PBC.

4. ALP $\geq 1.67 \times$ upper limit of normal (ULN) at Visit 1 and Visit 2 and with $< 30\%$ variance between the levels from Visit 1 to Visit 2.
5. Contraception: Female patients must be postmenopausal, surgically sterile, or if premenopausal, agree to use ≥ 1 effective method of contraception during the trial. Effective methods of contraception are considered to be Hormonal (e.g., contraceptive pill, patch, intramuscular implant or injection); or Double barrier method, i.e., (a) condom (male or female) or (b) diaphragm, with spermicide; or Intrauterine device (IUD); or Vasectomy (partner).
6. Must provide written informed consent and agree to comply with the trial protocol.

4.3 EXCLUSION CRITERIA

1. Consumption of >3 units of alcohol per day (>21 units per week) if male and >2 units of alcohol per day (>14 units per week) if female for at least 3 consecutive months in the last 5 years (Note: 1 unit = 12 ounces of beer, 4 ounces of wine or 1 ounce of spirits/hard liquor).
2. History or presence of other concomitant liver diseases including:
 - Hepatitis B or C virus (HCV, HBV) infection
 - Primary sclerosing cholangitis (PSC)
 - Alcoholic liver disease
 - Definite autoimmune liver disease or overlap syndrome
 - Non-alcoholic steatohepatitis (NASH)
3. Cirrhosis with complications, including history or presence of: spontaneous bacterial peritonitis, hepatocellular carcinoma, bilirubin $> 2 \times$ ULN, ascites, encephalopathy, known esophageal varices or history of variceal bleeding and active or history of hepatorenal syndrome.
4. History of any venous thromboembolism, TIA, intracranial hemorrhage, neoplasm, arteriovenous malformation, vasculitis, bleeding disorder, coagulation disorders or screening blood tests that indicate altered coagulability (e.g. platelet count, aPTT, PTT or TT tests).
5. Patients with INR $>$ ULN at visit 1.

6. Patients with total bilirubin > ULN at visit 1 that is not due to Gilbert's syndrome.
7. Patients with >30% increase in ALT, total bilirubin, or INR between Visit 1 to Visit 2, unless both results (visit 1 and visit 2) are within the reference range.
8. Patients with serum creatinine >ULN according to the gender at Visit 1.
9. Patients with abnormal total creatine kinase (CK) OR lipase OR amylase at Visit 1.
10. Unstable cardiovascular disease, including:
 - unstable angina, (i.e., new or worsening symptoms of coronary heart disease within the past 3 months), acute coronary syndrome within the past 6 months, acute myocardial infarction in the past 3 months or heart failure of New York Heart Association class (III – IV) or worsening congestive heart failure, or coronary artery intervention, within the past 6 months
 - history of (within prior 3 months) or current unstable cardiac dysrhythmias
 - uncontrolled hypertension (systolic blood pressure [BP] >160 mmHg and/or diastolic BP >100 mmHg)
 - stroke or transient ischemic attack within the prior 6 months
11. History of malignancy in the past 5 years and/or active neoplasm with the exception of resolved superficial nonmelanoma skin cancer.
12. Contraindications to Saroglitzaz magnesium or has any conditions affecting the ability to evaluate the effects of Saroglitzaz magnesium.
13. Known allergy, sensitivity or intolerance to the study drug, comparator or formulation ingredients.
14. Participation in any other clinical study within the previous 3 months of screening.
15. Illicit substance abuse within the past 6 months.
16. History or other evidence of severe illness or any other conditions that would make the patient, in the opinion of the investigator, unsuitable for the study (such as poorly controlled psychiatric disease, human immunodeficiency virus (HIV), coronary artery disease or active gastrointestinal conditions that might interfere with drug absorption).

4.4 WITHDRAWAL CRITERIA

The Investigator may withdraw a subject from the study for any of the following:

1. Subject who reports AE and if considered in Investigator's/Medical Expert's opinion that it is not in the subject's best interest to continue.
2. Any subject found to have entered the study in violation of this protocol.
3. Subject's lack of compliance to the study protocol.
4. Any subject who wishes to withdraw his / her consent for participation in the study.
5. In case a subject becomes pregnant, then she will be withdrawn from the trial.
6. Any subject who requires the use of unacceptable concomitant medications as mentioned in exclusion criteria (Section 4.3) and restrictions (Section 5.10).
7. Termination of study by sponsor, IRB/IEC, or the regulatory authority.

4.4.1 Discontinuation of Subject Investigational Product (IP)

Patients with worsening liver function will not be enrolled in the study. Evidence of worsening liver function will be assessed based on the 2 initial laboratory values used to establish the baseline.

Elevations in ALT and/or AST, occurring after the initiation of study drug, that meet the definition of a potential Case of Drug-Induced Liver Injury per below;

1. If patients with abnormal baseline liver indices develop elevations of AST or ALT greater than 2x baseline or total bilirubin greater than 1.5x baseline values while on study, testing shall be repeated within 48 -72 hours.
2. If there are persistent elevations in ALT or AST greater than 2x baseline or TBL greater than 1.5x baseline values, then close observation (testing and physical examination 2-3 times per week) shall be initiated or study drug will be discontinued
- A decision to discontinue or temporarily interrupt the study drug will be considered based on factors that include how much higher baseline ALT and AST were relative to the upper limit of normal (ULN) and how much the on study ALT and AST levels have increased relative to baseline, in addition to

whether there is concomitant elevation of bilirubin or INR. Study drug will be discontinued or temporarily interrupted:

- a. When the baseline values were < 2x ULN, discontinue if ALT or AST increases to > 5x baseline,
- b. When the baseline values were \geq 2x ULN but < 5x ULN, discontinue if ALT or AST increases to >3x baseline,
- c. When the baseline values were \geq 5x ULN, discontinue if ALT or AST increases to > 2x baseline,
- d. Discontinue if ALT or AST increase > 2x baseline AND the increase is accompanied by a concomitant TBL increase to >2x baseline OR the INR concomitantly increases by >0.2,
- e. In any patients with signs and symptoms of fatigue, nausea, vomiting, right upper quadrant pain or tenderness, fever, rash, and/or eosinophilia (> 5%).

- If a patient lives in a remote area, laboratory testing can be performed locally and the results shall be promptly communicated to the investigator site promptly.
- If patient develops an adverse event of grade 3 that is probably or possibly related to study drug and any patient regardless of attribution to drug who develops a grade 4 or higher Common Terminology Criteria for Adverse Event (CTCAE version 4.03).
- Parameters of renal function: IP is to be discontinued if the estimated glomerular filtration rate (eGFR) falls to <60 mL/min/1.73m² (calculated using Chronic Kidney Disease Epidemiology Collaboration (CKD-EPI) equation) and where the value is reconfirmed after 24 hrs repeat. Additionally, any subject who requires renal replacement therapy will also have IP discontinued.
- Patient will be immediately discontinued from study drug and followed until resolution of adverse event and laboratory values have returned to baseline, if any of the following criteria occur.

- a. TB \geq 3.0 mg/dL in individuals with normal baseline TB. In individuals with elevated baseline TB due to known Gilbert's syndrome, doubling of direct bilirubin will prompt immediate discontinuation of the study drug.
- b. Total CK $>$ 5x ULN
- c. Amylase and lipase $>$ ULN
- d. Hemoglobin $<$ 100 g/L or HCT $<$ 30%
- e. Platelets $<$ 100000/ μ L
- f. WBC $<$ 3.5 X 10⁹/L
- g. If more than 3 patients develop a CTCAE grade 3 or higher in the same category, or if 3 or more patients meet the above individual criteria (a to f) the trial may be stopped and/or unblended safety data will be evaluated.

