- Parameters of renal function: IP is to be discontinued if the estimated glomerular filtration rate (eGFR) falls to <60 mL/min/1.73m² (calculated using Chronic Kidney Disease Epidemiology Collaboration (CKD-EPI) equation) and where the value is reconfirmed after 24 hrs repeat. Additionally, any subject who requires renal replacement therapy will also have IP discontinued.
- Patient will be immediately discontinued from study drug and followed until resolution of adverse event and laboratory values have returned to baseline, if any of the following criteria occur.
 - a. TB \geq 3.0 mg/dL in individuals with normal baseline TB. In individuals with elevated baseline TB due to known Gilbert's syndrome, doubling of direct bilirubin will prompt immediate discontinuation of the study drug.
 - b. Total CK > 5x ULN
 - c. Amylase and lipase > ULN
 - d. Hemoglobin < 100 g/L or HCT <30%
 - e. Platelets < 100000/ μ L
 - f. WBC <3.5 X 10⁹/L
 - g. if more than 3 patients develop a CTCAE grade 3 or higher in the same category, or if 3 or more patients meet the above individual criteria (a to f) the trial may be stopped and/ or unblinded safety data will be evaluated

Excluded concomitant medications: Patients are not permitted to take thiazolidinedione (pioglitazone, rosiglitazone), chemotherapy, or other investigational medications during the study. Patients should not take any over-the-counter medications or complementary and/or alternative medications without prior consultation of the Investigator.

Permitted concomitant medications: With the exception of excluded concomitant medications, other medications that patients have been taking at stable dosages for at least 3 months before study entry. Statins are permitted as concomitant medications; however, patients will be monitored for statin related toxicity when it is co-administered. Glycemic control medications will be permitted as concomitant medications, including antidiabetic drugs such as metformin, sulfonylureas, dipeptidyl peptidase 4 (DPP-4) inhibitors and insulin. Patients must continue with their current drug regimen without any change in dosage.

Treatment for common illness during the study may be allowed.

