4.5 HANDLING OF PATIENT WITHDRAWAL

In case of withdrawal of consent, and unless otherwise stated by the patient in the informed consent form, Investigators will be encouraged to get information from the medical care provider, in order to follow the medical status of the patients (especially in cases where the patients have withdrawn their consent after having experienced an adverse event). Investigators will also be expected to try as much as possible to re-contact those patients at the end of the trial, in order to obtain status.

If subject discontinues from the study for any reason, before the End of Treatment Visit, the investigator will make all attempts to carry out all End of treatment Visit procedures.

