7 INVESTIGATIONAL PLAN

7.1 STUDY DESIGN AND PLAN

This is a Phase 2 prospective, multicentre, randomized, double-blind, placebo-controlled study includes a total 36 patients with a diagnosis of Primary Biliary Cholangitis. The study will be conducted over a period of up to 26 weeks and will include a 6-week Screening Phase, a 16-week Treatment Phase and a safety follow-up visit after 4 weeks.

Screening Phase:

- Visit 1 (Day -42): Patient eligibility for participation in the study will be assessed. Medical history will be obtained and physical examination, electrocardiogram (ECG) and laboratory evaluations (including serology, [anti-nuclear antibody, smooth muscle antibody and serum immunoglobulin level G], clinical chemistry, hematology, liver biochemistries, and urinalysis) will be performed. In patients with ANA or SMA antibody positive titers, a liver biopsy must have been performed to rule out autoimmune hepatitis or overlap syndrome. Female patients will undergo a pregnancy test. Serum ALP must be ≥ 1.67 upper limit of normal (ULN) to proceed further in the study.
- Visit 2 (Day -14 to -7): Liver biochemistries (ALT, ALP, total bilirubin (TB) and INR will be re-measured approximately 4 weeks from Day -42 to determine eligibility. Elevated ALP must be ≥ 1.67 ULN on 2 occasions in the Screening Phase and is necessary for study entry. If there is an increase of more than 30% in the levels of ALT, total bilirubin or INR at Day (-14) to Day (-7) [Visit 2] as compared to the values on Day (-42) [Visit 1], then such patients will not be eligible for study entry. The average of two assessments (Visit 1 and Visit 2) of liver biochemistries and INR will be considered as baseline values for these parameters.

Randomization & Treatment Phase:

- Visit 3: The Randomization & Treatment Phase will include 6 outpatient visits over a period of 16 weeks, including the randomization visit. Patients will be randomly assigned to receive either Saroglitzaz magnesium (2 mg or 4 mg) or placebo orally

once daily in addition to their ongoing treatment with UDCA (Patients unable to tolerate UDCA will receive only the investigational medicinal products), starting on Day 1 and continuing for 16 weeks. Efficacy and safety parameters will be assessed during each study visit as per the Schedule Visit Table 1.

- Visit 3.1: Patient will visit study site at 2 weeks after randomization visit for LFTs. The LFTs will be performed at local laboratory.

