8.3.1.3 Per-protocol population (PP)

The per-protocol population (PP) includes all randomized patients who meet all the inclusions/exclusion criteria, completed the treatment phase and have not deviated from or violated the protocol in such a way that could affect efficacy outcome.

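### Section 4.4.1 mandates a stop at absolute haemoglobin/haematocrit, platelet and WBC limits, but entry sets no matching numeric limits, and the text does not say whether a pre-dose value counts

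*Protocol*

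**What the plan says.** Protocol 4.4.1, and its copy in the synopsis, lists six laboratory limits, a to f, for which "Patient will be immediately discontinued from study drug and followed until resolution of adverse event and laboratory values have returned to baseline". Limit d reads "Hemoglobin < 100 g/L or HCT <30" per cent; e is platelets below 100000/µL; f is WBC below 3.5 x 10^9/L. None of d, e or f refers to the patient's own baseline. Item g then works at trial level: "if 3 or more patients meet the above individual criteria (a to f) the trial may be stopped", or unblinded safety data may be evaluated, or both.

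On entry, section 4.2 has no haematology criterion. In section 4.3, exclusion 4 covers "screening blood tests that indicate altered coagulability (e.g. platelet count, aPTT, PTT or TT tests") but gives no platelet number. Exclusion 12 covers contraindications and conditions that affect evaluation of the drug. Exclusion 16 leaves to judgement "any other conditions that would make the patient, in the opinion of the investigator, unsuitable for the study". Section 7.1 has the relevant tests taken at Visit 1: "clinical chemistry, hematology, liver biochemistries, and urinalysis) will be performed".

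**The concern.** A mandatory individual stop should not be capable of being met before the first dose by a patient whom the entry criteria admit. Here it can be, if the rule is read literally. A patient in any arm, placebo included, could be taken off drug for a stable value that says nothing about the drug, and could use one of the three counts in item g.

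There are consequences for the analysis. A stopped patient has not "completed the treatment phase and have not deviated from or violated the protocol", so leaves the per-protocol set (protocol 8.3.1.3), which is the only sensitivity analysis in SAP 6.5. The patient stays in MITT if there is a post-randomisation efficacy value. If the stop also leads to leaving the study, section 4.5 says "the investigator will make all attempts to carry out all End of treatment Visit procedures", and LOCF (protocol 8.3.1.2; SAP 6.4) would carry that early ALP to Week 16 in the primary analysis.

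With 36 patients over about 10 to 12 sites, roughly three per site, different readings could also lead to different handling of similar patients.

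**Working it through.** **Step 1. Stop limits against entry criteria.**

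| Limit in 4.4.1 | Depends on baseline? | Entry counterpart in 4.2–4.3 |
|---|---|---|
| a. Total bilirubin ≥3.0 mg/dL if baseline normal; doubling of direct bilirubin in Gilbert's syndrome | Yes | Exclusion 6: above ULN at Visit 1, except Gilbert's |
| b. Total CK >5x ULN | No | Exclusion 9: abnormal CK at Visit 1 |
| c. Amylase and lipase >ULN | No | Exclusion 9: abnormal lipase or amylase at Visit 1 |
| d. Hb <100 g/L or HCT <30% | No | None |
| e. Platelets <100000/µL | No | Exclusion 4 names platelet count, no number |
| f. WBC <3.5 x 10^9/L | No | None |

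Only d, e and f lack both a numeric entry limit and a baseline condition.

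**Step 2. Does the wording restrict d to f to on-study changes?** Pointing that way: the limits must 'occur', and follow-up runs until an adverse event resolves and values return to baseline, which makes little sense for a value already at baseline. Pointing the other way: nearby rules use explicit change words (ALT or AST 'increases', eGFR 'falls', patients 'develop' a grade 3 event), whereas item g counts patients who 'meet' a to f. Section 4.4.1 does not choose between the readings.

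**Step 3. Size.** The plan gives no figure to reproduce: SAP section 4 says that no formal sample size estimation was done, and neither document gives the share of eligible patients past d to f. The following is therefore conditional on an assumed share p, with N = 36 (protocol 4.1) and X ~ Binomial(36, p):

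- P(X ≥ 1) = 1 − (1 − p)^36
- P(X ≥ 3) = 1 − Σ(k = 0 to 2) C(36, k) p^k (1 − p)^(36 − k)

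At p = 2%: P(X ≥ 1) = 1 − 0.98^36 = 1 − 0.4832 = 0.517. P(X ≥ 3) = 1 − 0.4832 − 0.3550 − 0.1268 = 0.035.

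| Assumed p | At least one of 36 | At least three of 36 |
|---|---|---|
| 0.1% | 3.5% | under 0.001% |
| 1% | 30.4% | 0.6% |
| 2% | 51.7% | 3.5% |
| 3% | 66.6% | 9.3% |
| 5% | 84.2% | 26.8% |

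Here p is the share left after any exclusion by judgement. The documents support no row over another.

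**Step 4. Weight of one stop.** 1/12 = 8.3% of a planned arm. For comparison, the 20% dropout allowance in section 4.1 is 0.20 x 12 = 2.4 patients per arm.

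**The case against.** The strongest reply is that the on-study reading is the natural one. Besides the wording in step 2, section 9.4.1 says that a condition present at screening is not an adverse event unless it changes in severity or seriousness, so a stable low value would give nothing to resolve. This stands as the better reading, but it is an inference about a mandatory safety rule that each site must apply.

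Next, entry is not unguarded. Exclusion 3 removes complicated cirrhosis, exclusion 4 can catch a clearly low platelet count, and an investigator who knows the stop limits can see the Visit 1 haematology and use exclusion 12 or 16. This also stands. It narrows the group but sets no limit aligned with d, e or f.

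Third, the consequences are limited. The per-protocol analysis is supportive. Section 4.1 already allows for 20% dropout and adds patients beyond that. The LOCF effect arises only if a patient leaves the study and does not merely stop drug. A Data Monitoring Committee reviews safety data regularly (7.6) and could compare on-study values with baseline. All of this is right and keeps the point small.

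Finally, the schedule tables are not shown in the public copy, so a haematology check at Visit 3 before dosing can be neither confirmed nor excluded. That is not held against the plan.

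**Conclusion.** The mismatch is real and can be checked from the text: as written, the plan can randomise a patient already past d, e or f, and it does not say whether that patient must stop. It is a cheap improvement, not a threat to the trial's validity.

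A reader might go further and infer that item g is likely to halt the trial on pre-existing values alone. The documents do not support that. Item g is permissive, the wording leans towards on-study events, and three such patients are unlikely unless the share admitted exceeds about 2%, a share that the documents do not give. Nor do they support saying that platelets are ignored at entry, because exclusion 4 names them; what is missing is the number. The figure of about 8% of an arm is the weight of one stop if it happens, not an estimate of how often it would.

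**What to change.** Make two changes, in the synopsis as well as the body.

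1. Add entry limits to section 4.3, read from Visit 1: haemoglobin ≥100 g/L and haematocrit ≥30%, platelets ≥100000/µL, WBC ≥3.5 x 10^9/L.
2. State in section 4.4.1 that d, e and f, for both the individual stop and the count in item g, mean a value past the limit that is new or worsened from the last pre-dose value.

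The second change must cover both uses. Restricting only the item g count to patients who first cross a limit after dosing would leave the mandatory stop for someone whose value drifted past a limit between Visit 1 and the first dose. It would also drop from the count a patient just past a limit before dosing who then worsens markedly on drug.

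The cost is amendment wording and possibly a few more screen failures. No new test is needed, since haematology is already drawn at Visit 1. If no later pre-dose sample is scheduled, the reference value could be about six weeks old, because Visit 1 is at Day -42.
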